#### 9.1.3 Subsequent Surgical Interventions

The cause for subsequent surgical interventions should be listed as a serious adverse event.

Subsequent surgical interventions are classified as follows:

**Revision**: a procedure that adjusts or in any way modifies the original implant configuration. A revision may also include adjusting the position of the original configuration.

**Removal**: a procedure where all of the original system configuration are removed with or without replacement.

**Supplemental Fixation**: a procedure in which additional instrumentation not under study in the protocol is implanted.

**Reoperation**: any surgical procedure at the involved level that does not require removal, modification, or addition of any components to the system.

## 9.2 Adverse Event Reporting

Any AE that occurs during the subject's participation in the study will be recorded on the Adverse Event case report form. Pre-existing medical conditions or symptoms occurring prior to the initiation of the study will not be reported as AEs but a worsening of a pre-existing medical condition or symptom will be reported as an AE. Pain, neurological status and functional impairment should be considered AEs when a subject's complaint for any of these symptoms results in an unscheduled visit or when a subject presents with new or worsening symptoms as compared to a previous visit.

All AEs will be followed until the event is resolved or considered to be stable. Relevant source documentation must be available to confirm the occurrence of an AE and must be provided to the sponsor upon request.

### 9.2.1 Serious Adverse Event Reporting

Independent of the relationship to the study device or device procedure, the site must report SAEs to the Sponsor immediately upon becoming aware of the events and subsequently submit the appropriate CRFs within 10 working days. SAEs will be investigated and reported to the FDA if they fall within the appropriate guidelines for Medical Device Reporting (MDR). The site must also report SAEs to the reviewing Institutional Review Board (IRB)/Ethics Committee (EC) according to IRB/EC requirements.

The site must confirm the SAE in appropriate source documents and provide detailed information pertaining to the event to the sponsor and reviewing IRB/EC if requested.

## 9.3 Adverse Event Severity

The Investigator will be asked to characterize the severity of each AE as mild, moderate or severe. The assessment is subjective and the Investigator will use medical judgment to compare the reported AE to similar types of events observed in clinical practice. Guidelines for AE severity assessment are as follows:

**Mild:** The AE is transient and easily tolerated by the subject. No medical treatment required.

**Moderate:** The AE causes the subject discomfort and interrupts the subject's usual activities. Medical treatment required to alleviate or lessen the impact of this untoward condition.

**Severe:** The AE causes considerable interference with the subject's usual activities may be incapacitating and may require hospitalization. See **Section 9.1.2. Serious Adverse Events.**

## 9.4 Adverse Event Association

The relationship of all AEs to the device, the procedure or general surgery will be classified by the Investigator as not related, possibly related, probably related or definitely related.

**Not related:** The AE is due to an underlying or concurrent illness or effect of another device, drug or intervention and is not related to the study device, procedure or general surgery.

**Possibly related:** The causal and/or temporal relationship to the study device, procedure or general surgery, is equally or less likely than other plausible explanations.

**Probably related:** The causal and/or temporal relationship to the study device, procedure or general surgery, is likely or significantly more likely than other plausible explanations.

**Definitely related:** A clinical event that can only be attributed to the device, procedure or general surgery.

## 9.5 Potential Risks and Anticipated Adverse Events

### 9.5.1 General Surgery Risks

General surgical risks are but may not be limited to:

- Airway Obstruction
- Anaphylaxis
- Anesthesia Related
- Atelectasis
- Blood Clots, including Pulmonary Emboli
- Cardiac Arrest
- Cardiac, Other
- CVA
- Death
- Decompensation
- Deep Vein Thrombosis
- Epidural Fibrosis
- Epidural Hematoma or Bleeding
- Excessive Blood Loss
- Hemorrhage Possibly Requiring a Blood Transfusion
- Infection, Deep Wound
- Infection, Superficial Wound
- Infection, Urinary Tract
- Infection, Other
- Myocardial Infarction
- Phlebitis
- Pleural Effusion
- Pneumonia
- Pneumothorax
- Poor Tissue Healing
- Retained Sponge
- Septicemia
- Suture Abscess
- Transfusion Reaction
- Vascular or Blood Vessel Injury
- Wound Dehiscence

### 9.5.2 Lateral Access and with or without Supplemental Fixation for Fusion Surgery Risks

Lateral Access with or without Supplemental Fixation for Fusion surgical risks are but may not be limited to:

- Allergic Reaction to the Implant/Retractor Materials
- Bowel or Bladder Dysfunction
- Disc Height Loss
- Dural Tear (with or without Cerebrospinal Fluid Leak)
- Dysesthesia or Numbness
- Erosion due to Implant
- Failure to Relieve Symptoms, including Unresolved Pain
- Foot Drop
- Foreign Body Reaction
- Genital Numbness
- Kyphosis or Hyper-Extension
- Loss of Spinal Flexibility
- Muscle and Tissue Injury or Damage
- Nerve Injury
- Nerve Root Injury
- Osteolysis
- Pain, New Onset
- Pain, Unresolved
- Paralysis
- Pseudoarthrosis
- Sexual Dysfunction
- Spinal Cord Damage
- Spinal Degeneration
- Spinous Process Fracture
- Surgical Intervention at Incorrect Levels
- Tingling
- Thigh Pain
- Vertebral Body Fracture
- Weakness

### 9.5.3 K2M Device Risks

Risks specific to the RAVINE, ALEUTIAN Lateral, CASCADIA Lateral, SERENGETI, DENALI Minimally Invasive, EVEREST Minimally Invasive, and CAYMAN Minimally Invasive Systems are but may not be limited to:

- Bone Graft Migration
- Bone Graft Subsidence
- Device Instability
- Device Malposition
- Device Migration
- Device Subsidence
- Disengagement – from Bone
- Disengagement – Screw/Rod Interface
- Foreign Body Reaction
- Material Degradation
- Plate Breakage
- Prominent Implants
- Retractor breakage
- Rod Breakage
- Rod Interface Disengagement
- Screw Back-out
- Screw Breakage
- Screw/Rod Interface Slide
- Set Screw Loosening

## 10 SITE REGULATORY REQUIREMENTS

### 10.1 Institutional Review Board (IRB)/Ethics Committee (EC) Approval

Prior to enrolling subjects in the study, site IRB/EC approval must be obtained according to 21 CFR Part 56. IRB/EC approval must be maintained by the site throughout the study. The IRB/EC approval letter(s) must be maintained in the study files at all times.

### 10.2 Study Specific Informed Consent

The informed consent process when executed properly provides sufficient information about study procedures so that a potential participant can voluntarily make a reasonable decision about participation, based on an understanding of the purpose, potential risks and anticipated benefits (if any) of the study. Informed consent is not a waiver of rights.

A study specific sample informed consent will be provided to each site prior to the IRB/EC process. The sample informed consent should be used as a template for creating the IRB/EC specific informed consent. Prior to submission of the proposed informed consent to the reviewing IRB/EC, the Sponsor must review the informed consent for completeness according to the protocol and according to 21 CFR Part 50. Potential study subjects should be offered informed consent according to the process outlined in **Section 8.1 Patient Screening and Enrollment**.

Patients must not be offered informed consent until written proof of IRB/EC approval is attained. The patient should be given the opportunity to take home a copy of the informed consent to review and discuss with family members or acquaintances prior to signing. Potential study subjects must also be given the opportunity to discuss the procedure, risks, benefits, alternative treatments and study requirements prior to signing the informed consent. Patients should be informed that they are free to refuse participation in this study and refusal will not affect their medical treatment. If patients elect to participate, it should be made clear that they may withdraw from the study for any reason and at any time without prejudicing further care.

A copy of the signed and dated IRB/EC approved informed consent should be given to all subjects.

### 10.3 Regulatory Documents

Prior to patient enrollment, the following documents must be provided to the Sponsor and be on file at the site:

- Curriculum vitae and copy of medical license for Principal and Sub-Investigators
- IRB/EC approval letter and IRB/EC roster
- IRB/EC approved informed consent form
- Signed Clinical Research Agreement
- Signed Investigators Agreement for Principal and Sub-Investigators, as required
- Finalized budget agreement
- Financial disclosures for the Principal and Sub-Investigators
- Site Initiation documentation

## 11 SITE VISIT/MONITORING PROCEDURES

Monitoring of the study will be a continuous process conducted in accordance with 21 CFR 812.46 and applicable Sponsor procedures. Monitoring will be performed by qualified clinical research personnel, or designees, of K2M.

### 11.1 Site Qualification Visit

Prior to selecting an Investigator for participation in the study a Qualification visit will be performed. The purpose of the visit is to confirm that the Investigator/investigative site has adequate staff, including a designated Study Coordinator, and facilities to perform the study according to the requirements of the protocol.

### 11.2 Study Initiation Visit

Prior to enrolling subjects at a study site, a Site Initiation Visit will be performed. The purpose of the visit is to confirm that the site continues to be qualified for participation and to review the Investigator/site responsibilities and requirements for the study. Site training will be performed and will include:

- Review of the clinical protocol and data collection process
- Monitoring requirements
- IRB/EC requirements
- Informed Consent process
- Review of site records

### 11.3 Periodic Monitoring Visits

Periodic site monitoring visits will be performed during the study by a designated study monitor assigned by the Sponsor. The purposes of the visits are to confirm compliance to the protocol, review regulatory documents, accurate and complete records are being maintained and to compare source documents to completed CRFs for completeness and consistency. The initial monitoring visit to a site will be scheduled soon after the first 2 to 5 patients are enrolled in the study and may occur prior to the first surgery. The frequency of subsequent visits will be dependent upon the rate of enrollment and site performance on previous monitoring visits. If possible, monitoring visits will be performed at least quarterly. Specific assessments during a monitoring visit include:

- Continued site acceptability
- Compliance to the protocol
- IRB/EC approval status
- Use of the approved informed consent
- Adequacy of source documents
- Complete and accurate CRFs
- Reporting of adverse events
- Protocol deviations
- Site records

If it is determined during a monitoring visit that there are significant non-compliance issues at a site, including adherence to the protocol or applicable regulatory requirements, the issues will be discussed with the Investigator and Study Coordinator and the site will be instructed how to gain compliance. If continued non-compliance is detected on a subsequent monitoring visit, it may be necessary to terminate site participation in the study.

## 11.4 Final Close-Out Visit

At the completion of the last long-term follow-up visit at each site a final close-out visit will be performed. The purpose of the visit will be to:

- Review site records
- Reconcile all outstanding data queries
- Review the records retention requirements for the study
- Review the final IRB/EC requirements for the study

## 12 STATISTICAL METHODS

### 12.1 Study Design

Prospective single-arm controlled, multi-center study to evaluate the patient outcomes and incidence of complications using RAVINE compared to the literature reported results with the XLIF system for the surgical treatment of patients with symptomatic DDD with up to Grade 1 spondylolisthesis.

### 12.2 Study Hypothesis

The primary effectiveness endpoint is the improvement Back VAS and Leg VAS at 24 months as compared to pre-op time periods. The primary hypothesis of this trial is that the clinical performance of the K2M RAVINE system is non-inferior to the clinical performance achieved and reported with the NuVasive lateral system.

A PubMed literature review was conducted to assemble relevant publications utilizing results from minimally-invasive far lateral fusion surgeries utilizing the XLIF system in patients with symptomatic DDD with up to Grade 1 spondylolisthesis. Searches included all peer-reviewed journals published between January 2000 and April 2013. Articles were selected for review if at least a portion of the represented cases included minimally-invasive far lateral surgery with or without minimally-invasive supplemental stabilization. Sample sizes, patient populations, evaluated variables, results, and recorded complications were assessed for each selected article.

Only data regarding VAS back and leg outcomes of XLIF cases in patients with symptomatic DDD with up to Grade 1 spondylolisthesis were incorporated into the VAS score tables used for statistical analysis. Articles were entirely excluded from the statistical analysis if results combined data from cases with multiple diagnoses not included in this study or if data were extracted through meta-analysis.

The following tables give the VAS Back and VAS Leg improvements found from included studies:

#### VAS back

Paper #	n	Preop	Last FU	Difference of means	Weighted difference	Sum of weighted differences	Sum of sample sizes	Average difference of means
1 	30	3.90	2.90	1.00	30.00	889.53	237	3.75
2 	84	5.89	1.37	4.52	379.68			
3 	93	7.25	2.80	4.45	413.85			
4 	30	6.80	4.60	2.20	66.00			

#### VAS leg

Paper #	n	Preop	Last FU	Difference of means	Weighted difference	Sum of weighted differences	Sum of sample sizes	Average difference of means
1	30	7.50	2.90	4.60	138.00	560.10	153	3.66
2 **								
3	93	5.80	2.10	3.70	344.10			
4	30	5.40	2.80	2.60	78.00			

\*\* No Leg VAS separately detailed in paper for this study

The study hypothesis for both the Back and the Leg VAS is that the RAVINE system is non-inferior to other systems post-surgery. The hypotheses can be written:

H0:  $\mu_R \leq \text{OPC}$

H1:  $\mu_R > \text{OPC}$

where  $\mu_R$  is the mean VAS of the RAVINE system, the Objective Performance Criteria (OPC) is 3.25.

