### 12.3 Sample Size

A total sample size of 222 subjects was selected for the study. Assuming the true mean difference between pre-op and 24 month follow-up VAS is 3.66 and the standard deviation is 2.0, a sample size of 189 subjects provides >87% power to detect a statistically significant difference between the mean post-op VAS and the OPC of 3.25 using a one-sided one-sample t-test at a significance level of 0.05. In order to account for approximately 15% attrition, based on clinical experience, 222 subjects will be enrolled.

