### 12.5 Analysis of Primary Endpoint

The primary effectiveness endpoint will be evaluated on the Per Protocol population by a one-sided one-sample t-test of the RAVINE system which is measured as the difference between the pre-op and 24 month post-op Back VAS and the Leg VAS as compared to 3.25, the literature reported differences.

As secondary analyses, the comparison of the difference between the pre-op and 24 month Back VAS and Leg VAS will be repeated as follows:

- Considering ITT subjects with available 12 or 24 month data only. In the event that a subject has 12 month data but no 24 month data, the 12 month VAS scores will be used. Subjects without 12 or 24 month VAS measurements will be excluded.
- A Last Observation Carried Forward (LOCF) approach for all ITT subjects

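### The t-test against a fixed 3.25 shows only that mean improvement exceeds 3.25; with no stated margin, no derivation of 3.25 and no literature uncertainty carried, it does not by itself support non-inferiority to XLIF

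*Combined protocol and SAP*

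**What the plan says.** Section 12.2 puts the primary hypothesis as RAVINE being "non-inferior to the clinical performance achieved and reported with the NuVasive lateral system". Beneath the VAS leg table it repeats the claim for each scale: "The study hypothesis for both the Back and the Leg VAS is that the RAVINE system is non-inferior to other systems post-surgery". The formal hypotheses then set the RAVINE mean against one constant for both scales: "the Objective Performance Criteria (OPC) is 3.25".

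Section 12.3 sizes the trial on that constant, "using a one-sided one-sample t-test at a significance level of 0.05". Section 12.5 runs the same test and describes the comparator with the words "as compared to 3.25, the literature reported differences".

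The two literature tables in Section 12.2 pool by sample size only. They give a Back mean of 3.75 (four series, 237 patients) and a Leg mean of 3.66 (three series, 153 patients). They show no SD, standard error, interval or measure of heterogeneity. No non-inferiority margin is stated and the route from 3.75 and 3.66 to 3.25 is not given. The secondary analyses in Section 12.5 vary only how missing RAVINE scores are handled; none varies 3.25.

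**The concern.** A test against a constant answers one question: is the RAVINE mean improvement above 3.25? To go on to non-inferiority to XLIF, a reader needs to know how much worse than XLIF still counts as non-inferior, and how well XLIF performance is known. The plan supplies neither.

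If the trial succeeds, the result could be reported as non-inferiority to a named competitor at a one-sided 5% level. The design has not shown that it has that property. The Section 12.5 wording makes the slip easier, because it presents 3.25 as what the literature reported, while the tables report 3.75 and 3.66.

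**Working it through.** **1. The plan's own figure.** Section 12.3 assumes a true improvement of 3.66, an SD of 2.0 and 189 evaluable subjects. The trial standard error is SE_R = 2.0/√189 = 0.1455. The difference to detect is 3.66 − 3.25 = 0.41. The noncentral t gives 87.8% power, so "a sample size of 189 subjects provides >87% power" reproduces. For the null as written (mean no greater than 3.25), the size is exactly 5%.

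**2. What the tables show without any assumption.**

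| | Back | Leg |
|---|---|---|
| Series improvements (n) | 1.00 (30), 4.52 (84), 4.45 (93), 2.20 (30) | 4.60 (30), 3.70 (93), 2.60 (30) |
| n-weighted mean | 889.53/237 = 3.75 | 560.10/153 = 3.66 |
| Simple mean | 12.17/4 = 3.04 | 10.90/3 = 3.63 |
| Leave-one-out n-weighted means | 4.15, 3.33, 3.30, 3.98 | 3.43, 3.60, 3.92 |
| Gap g, n-weighted mean minus 3.25 | 0.50 | 0.41 |

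For Back, the gap between 3.25 and XLIF performance runs from 4.15 − 3.25 = 0.90 to 3.04 − 3.25 = −0.21, depending only on how the four papers are combined.

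**3. Conditional illustration.** Two inputs are assumptions because the documents give neither: the margin M, first set equal to the gap g, and the literature SD, set to 2.0 (range 1.5 to 3.0). If RAVINE is truly worse than XLIF by exactly M, the chance of passing is

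error = 1 − Φ[(1.653·SE_R + M − g)/√(SE_R² + SE_L²)],

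with 1.653 the one-sided 5% t value on 188 df, and SE_L the standard error of the n-weighted literature mean.

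*Sampling error only*, M = g:
- Back: SE_L = 2/√237 = 0.130. Error = 1 − Φ(0.2405/0.195) = 10.9% (8.5% to 16.1% over the SD range).
- Leg: SE_L = 2/√153 = 0.162. Error = 1 − Φ(0.2405/0.2175) = 13.4% (10.2% to 19.8%).

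*With between-paper variance* (DerSimonian-Laird, weights n/SD²), M = g:
- Back: Q = 98.6 on 3 df, I² = 97%, τ² = (98.6 − 3)/40.78 = 2.34. With Σ(n/237)² = 0.312, SE_L = √(4/237 + 0.312 × 2.34) = 0.86. Error is about 39%.
- Leg: Q = 15.1 on 2 df, I² = 87%, τ² = (15.1 − 2)/21.18 = 0.62. With Σ(n/153)² = 0.446, SE_L = √(4/153 + 0.446 × 0.62) = 0.55. Error is about 34%.
- Using the standard errors of the random-effects means instead (0.78 and 0.49) gives 38% and 32%.

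**4. Dependence on the margin** (literature SD 2.0).

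| Margin M | Variance carried | Back | Leg |
|---|---|---|---|
| 0.50 / 0.41 (the gap) | sampling only | 11% | 13% |
| 0.50 / 0.41 (the gap) | plus between-paper | 38–39% | 32–34% |
| 0.75 | sampling only | 0.6% | 0.4% |
| 1.0 | plus between-paper | 18–20% | 5–7% |

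**5. Power of a formal comparison** at the gap margin if RAVINE truly equals XLIF: Φ[g/√(SE_R² + SE_L²) − 1.645]. With sampling error only this is Φ(0.503/0.195 − 1.645) = 82% for Back and Φ(0.411/0.2175 − 1.645) = 60% for Leg. With between-paper variance it is 14–16% for Back and 18–20% for Leg.

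**The case against.** The strongest reply is that the test is correctly specified. The written null is about 3.25, Sections 12.3 and 12.5 test exactly that, and a fixed performance goal is an accepted convention. The phrase about performance achieved and reported could even mean the published benchmark itself rather than a true XLIF mean. All of this stands as a defence of the test. It does not defend the non-inferiority wording, since even the published benchmarks are 3.75 and 3.66, and nothing explains why 3.25 is close enough to them.

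A reader might infer that the 5% error rate simply fails for any claim about XLIF. The documents do not support that. They state no margin, and 3.25 may already include a cushion for literature uncertainty. At a margin of 0.75, sampling error alone leaves the error below 1%. At 1.0, even with between-paper variance, the Leg error is near its nominal level.

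A reader might also infer that 3.25 is too lenient for Back. The simple mean (3.04) and the random-effects mean (3.07) both lie below 3.25. If XLIF truly sits there, 3.25 is a harder bar than parity. Every leave-one-out Back mean, by contrast, lies above 3.25. So the direction is not established.

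Two further cautions stand. Between-paper variance from three or four papers is itself imprecise. And the Back series with an improvement of 1.00 began at a pre-operative mean of 3.90, so its mean could not have fallen by more than 3.90. Differences in baseline may explain part of the spread, and a wider interval does not correct for that.

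**Conclusion.** The concern holds as a mismatch between claim and test. The 5% one-sided error is controlled for mean improvement exceeding 3.25. Nothing in the plan links that result to non-inferiority to XLIF: no margin, no derivation of 3.25, no allowance for literature uncertainty, and no sensitivity analysis over the constant. This part rests on the text and tables alone.

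The error rates are illustrations. About 11% (Back) and 13% (Leg), and the order of 30% to 40% with between-paper variance, hold only if the margin is the gap to 3.25 and the literature SD is near 2.0. They do not show that the planned t-test is invalid. This should be corrected before results are reported, but it does not call for a redesign.

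**What to change.** Keep the one-sample t-test and the sample size, and make these changes:

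- In Sections 12.2 and 12.5, restate the primary conclusion as: *mean improvement exceeds a fixed performance goal of 3.25 derived from the literature*. Record how 3.25 was reached.
- In Section 12.5, stop describing 3.25 as the literature result; cite 3.75 (Back) and 3.66 (Leg) as the pooled values.
- Add one supportive, non-gating table per scale. It should show RAVINE minus pooled literature improvement, with an interval that carries literature sampling error and between-paper variance, plus leave-one-paper-out results. Any SD assumed for the papers should be stated, with a range.

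The cost is wording, two tables and a narrower headline claim; no extra patients are needed. The table should not serve as a formal non-inferiority test. At the gap margin such a test would have about 82% (Back) and 60% (Leg) power with literature sampling error only, and about 14% to 20% once between-paper variance is included.
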